A post-study interview with the woman will be conducted once she is stable and prior to her discharge from the study hospital. Women will be interviewed and asked about their experience with pain and side effects. Women will be asked to rate their overall experience on a categorical five-point scale from 'very unsatisfied' to 'very satisfied'. Instruments will be informed by prior research on the acceptability of new medical technologies for delivery of magnesium sulphate among Indian women.

Data will be collected throughout the woman's admission, with data collection stopping postnatally at time of discharge or maternal death. No further follow-up is planned.

Pilot Study

Given the uncertainty of the effect of each of these drugs on this population, we will conduct a pilot study (n=30) prior to the start of the trial. The purpose of this pilot is to test the feasibility of the study protocol as designed. Women will be allocated serially to one of three oral antihypertensive regimens regimens: methyldopa (n=10), labetalol (n=10), or nifedipine (n=10).

The primary aim of the pilot study is to assess the three proposed drug regimens and, potentially, reveal the need for a lower dose. Methyldopa may not be effective for acute control of severe hypertension. However, in many settings where labetalol or nifedipine are not available, methyldopa is the oral drug of choice. Given our concerns about the slow onset and general lack of potency of

methyldopa, we are conducting a pilot study to assess whether it is appropriate to include it in the trial. If the success rate in any of the three arms is less than 30% (3/10) then the investigators will assess whether to include the regimen in the RCT. The secondary aims of the pilot are to (1) assess adverse outcomes and necessity for additional antihypertensive treatment among women in the three study arms; and (2) to evaluate data collection tools (including use of the Glasgow Coma Scale and assessments of women's attitudes post-treatment) in the subsequent trial.

Required ethical approvals for the pilot study have been obtained from Government Medical College Nagpur and the University of British Columbia.

Study Assessment and Data Collection Forms

Form 1: Screening Form. This form will determine a woman's eligibility for enrollment in the study. The form will also document basic demographic characteristics and obstetrical history.

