We hypothesize that nifedipine treatment of hypertensive parturient women will be more effective than labetalol or methyldopa in controlling high blood pressure (defined as 120-150mmHg systolic and 70-100 mm Hg diastolic) within 6h. Brown et al found that 83% of pregnant women with severe hypertension treated with nifedipine had successful lowering of blood pressure 110 to 169/80 to 109 mm Hg by 90 minutes without an adverse outcome.¹⁷ Our trial will enroll sicker patients and our goal is lower and lasting control. Based on the (scant) available literature, we hypothesize that nifedipine will control 75% of high blood

pressure within 6 hours and labetalol and methyldopa will be able to control 62.5% and 62.5%, respectively. As the subjects in the nifedipine study group will serve as a comparison group for both the labetalol and methyldopa regimens, the comparison of labetalol and nifedipine requires a sample size of 261 in each study group given a two tailed test, $\alpha=0.05$ and $1-\beta=80\%$, and a simple Bonferroni correction. Using the same statistical assumptions, with a nifedipine sample size of 261, the methyldopa study group requires 261 subjects. In order to account for loss to follow-up, we will enroll 894 women total (nifedipine: 298 women; labetalol: 298 women; methyldopa: 298 women).

Proposed Analyses

After the data are entered, they will be converted into an SPSS for Windows data file, reviewed for logical inconsistencies, cleaned, and analyzed.

For each of the regimens, we will calculate the following statistics:

- % of women who reach the target (defined as 120-150mmHg systolic and 70-100 mmHg mm Hg diastolic) within 6h without any specified adverse outcome (see above)
- % of women who reach the target (defined as 120-150mmHg systolic and 70-100 mmHg mm Hg diastolic) within 3h without any specified adverse outcome (see above)
- % of women who experience an adverse outcome. Adverse outcomes include hypotension (systolic blood pressure, <120 mm Hg and/or diastolic blood pressure <70 mm Hg and fetal compromise), caesarean section for fetal distress, severe headache or eclampsia.

- % of women who reach an intermediate target (defined as 120-159 mmHg systolic and 70-104 mmHg diastolic) within 6 hours without an adverse outcome.
- % of time systolic and diastolic blood pressure in target range

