At each hospital, patient files will be kept in locked cabinets with all identifying information removed. Signed informed consent forms will also be kept in locked cabinets, separate from the patient files. Only authorized study personnel will have access to these files. The original copy of all study forms will be sent to Gynuity Health Projects on a monthly basis and photocopies of each form will be maintained at each study hospital for five years.

Confidentiality

All evaluation forms and records will be identified using a coded number to maintain participant confidentiality. All records will be kept in a locked filing cabinet at the study hospital. Clinical information will not be released without the permission of the participant, except as required for monitoring by Gynuity Health Projects.

Data Monitoring Committee

An independent Data Safety Monitoring Board (DSMB) will be established to oversee the safety of participants in the trial. The terms of reference of the DSMB will be developed separately, based on the principles developed by the DAMOCLES group.

For safety purposes, interim analyses will be conducted when approximately half of the study sample have been enrolled (n=447). Recommendations will be made based on any findings of differences in primary outcomes or adverse events between the three study groups. The Haybittle–Peto boundary will guide the interim analysis and statistical stopping approach: If the interim analysis shows a probability of less than 0.001 that the primary outcome of the three treatments are different, then the trial will be stopped early. It is possible that only one arm might be discontinued without the need to discontinue the entire trial in the event of a safety issue in that arm.

As indicated above, the primary outcome is defined as the % of women who reach the target (defined as 120-150mmHg systolic and 70-100 mmHg mm Hg diastolic) at 6h without any specified adverse outcome.

REPORTING, PUBLICATIONS AND NOTIFICATION OF RESULTS

Data Policy

The data from this study will be confidential until the database is closed at the end of the study. Following this the study investigators will have exclusive access to the data until the publication of the results in a journal. The consent form will include a clause for the woman to give permission for her anonymous data to be used for future research studies.

Publication

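### The interim stopping rule is worded in reverse and treats the three arms as one question, although the trial is sized for two separate comparisons with nifedipine

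*Protocol*

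**What the plan says.** The Data Monitoring Committee section sets one interim analysis at about half of enrolment (n=447), names the Haybittle-Peto boundary as the guide, and says that the trial will stop early "If the interim analysis shows a probability of less than 0.001 that the primary outcome of the three treatments are different". It names no test. It adds that a single arm may be closed without the need to "discontinue the entire trial in the event of a safety issue in that arm". No arm-level provision is made for a difference in the primary outcome.

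The Sample Size Calculation section is built differently. There, "the nifedipine study group will serve as a comparison group for both the labetalol and methyldopa regimens", at two-sided alpha 0.05 with 80% power "and a simple Bonferroni correction". The assumed success rates are 75% for nifedipine, while "labetalol and methyldopa will be able to control 62.5% and 62.5%, respectively". This gives 261 women per arm, raised to 298 per arm (894 in total) for loss to follow-up.

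The Pilot Study section records "our concerns about the slow onset and general lack of potency of" methyldopa, and says that any regimen with pilot success below 30% (3 of 10) will be reconsidered for the trial.

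**The concern.** There are two faults of different weight.

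First, taken literally, the condition is met when a difference between treatments has been almost ruled out. A Haybittle-Peto rule works the other way: it stops when the data would be very unlikely if the treatments were equal.

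Second, the rule does not fit the design. The trial asks two questions, nifedipine v labetalol and nifedipine v methyldopa, each sized on its own. The interim rule asks one question of all three arms and has one consequence, ending the trial. It does not say what happens when only one comparison is decisive. If methyldopa performs clearly worse than planned, which the protocol itself regards as possible, the boundary can be crossed because of that arm alone. Nifedipine v labetalol would then end with about half of its planned women.

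**Working it through.** **Inputs from the protocol.** Success rates 75 / 62.5 / 62.5% (nifedipine / labetalol / methyldopa); two-sided alpha 0.05 split over two comparisons, so 0.025 each; power 80%; 261 evaluable and 298 enrolled per arm; interim at 447 women; threshold 0.001.

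**Assumptions.** Methyldopa rates of 55% and 50%; a Pearson chi-square test with 2 df as the three-arm test; equal numbers per arm at the interim.

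**1. The planned sample size.** With the pooled-variance formula,

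n = [z(0.9875)·√(2·p̄(1−p̄)) + z(0.80)·√(p1(1−p1)+p2(1−p2))]² / (p1−p2)²

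where p1 = 0.75, p2 = 0.625 and p̄ = 0.6875:

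n = [2.2414×0.6555 + 0.8416×0.6495]² / 0.125² = 4.064 / 0.015625 ≈ 260.1, rounded up to 261.

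This matches the protocol exactly and confirms that the design is two pairwise comparisons at 0.025 each. At alpha 0.05 without correction the formula gives 215.

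**2. Numbers at the interim.** 447 / 3 = 149 enrolled per arm. The allowance for loss is 1 − 261/298 = 12.4%. If that loss already applied at the interim (an assumption), 149 × 0.876 ≈ 130 per arm would be evaluable.

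**3. Chance of stopping under a three-arm test.** In each simulated interim (at least 400,000 per scenario), successes are drawn as binomial for each arm. The trial stops if the 2-df chi-square exceeds 13.82 (p<0.001). The nifedipine v labetalol p-value from the pooled z test is then compared with 0.025.

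| True rates, % (N / L / M) | Stops, 149 per arm | Stopped trials with N v L p≥0.025 | All trials that stop with N v L p≥0.025 | Stops, 130 per arm |
|---|---|---|---|---|
| 75 / 62.5 / 62.5 (planned) | 17% | 6% | about 1% | 13% |
| 75 / 62.5 / 55 (assumed) | 53% | 27% | 15% | 43% |
| 75 / 62.5 / 50 (assumed) | 82% | 39% | 32% | 73% |

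The fourth column is the product of the two before it, from unrounded values: 0.1735 × 0.064 = 0.011; 0.529 × 0.275 = 0.145; 0.816 × 0.390 = 0.318.

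**4. If pairwise tests were meant.** Suppose that either comparison with nifedipine at p<0.001 stops the trial. At 149 per arm, stopping is then 26% at the planned rates and 89% at 75 / 62.5 / 50. In the latter case 42% of stopped trials have nifedipine v labetalol at p≥0.025. The fault therefore does not depend on which test was intended; it comes from tying a single crossing to the whole trial.

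**The case against.** The strongest reply has four parts.

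- **The inversion is a slip.** The boundary is named in the same sentence and 0.001 is the threshold attached to it. A reader might infer that the board would stop a trial that shows no difference; the reference to Haybittle-Peto does not support that. This stands, so the first fault is editorial.
- **The harm depends on assumed rates.** A reader might infer that the likeliest crossing leaves nifedipine v labetalol unanswered. In general it does not. At the planned rates 94% of stopped trials already have that comparison below 0.025, and at 75 / 62.5 / 50 it is 61%. An extreme case such as 75 / 75 / 50, where 95% of trials stop, abandons the protocol's own hypothesis that nifedipine is better than labetalol. Nor is the unconditional power of about 53% at 149 per arm the right measure of loss, because it does not condition on the trial having stopped. This also stands.
- **There is room for judgement.** The boundary is described as a guide, the board makes recommendations, and its terms of reference are to be written separately. A board might also treat failure to control blood pressure as an arm-level safety issue. This stands only in part. The stopping sentence itself says that the trial will stop, and the section deals with primary-outcome differences and single-arm safety in separate sentences. Separate terms of reference can add detail, but they should not have to overturn a rule that the protocol states.
- **The pilot screens methyldopa.** It does, but the trigger is success below 30%. It is not designed to catch an arm at 50% or 55%.

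**Conclusion.** The point holds as a mismatch between a stated interim rule and the stated design, together with an inverted sentence. It is not a matter of missing detail. At the planned rates the cost is small: 17% of trials stop, and about 1% of all trials stop without nifedipine v labetalol reaching 0.025. It grows if methyldopa does worse than planned, to 15% of all trials at 55% success and 32% at 50%. Those two rates are assumptions, prompted by the protocol's doubt about potency and not given in it. The figures also assume a 2-df chi-square and 149 evaluable per arm; with about 130 per arm, stopping falls to 13%, 43% and 73% in the three cases. That a three-arm test is intended is an inference, but a pairwise reading leaves the same fault. Should-fix, to be settled before the look at n=447, because a choice made after seeing those data would be data-driven.

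**What to change.** In the Data Monitoring Committee section and in the board's terms of reference, replace the stopping sentence with a rule to this effect:

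- At n=447, nifedipine v labetalol and nifedipine v methyldopa are each assessed separately on the primary outcome.
- The boundary is a two-sided p-value below 0.001 against equality.
- A crossing in one comparison leads to a board recommendation on that comparison only; the other continues to its planned size.
- The whole trial stops for efficacy only if both comparisons cross.

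The existing provision for a safety issue in one arm can stay as it is.

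The cost is a change of wording and one more test at the interim. The final alpha is essentially unchanged: the interim look can add at most 0.001 to the 0.025 allotted to each comparison. The sample size does not change.
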